#### Culturally Tailored Smoking Cessation Treatment + Adherence Enhancement

The CTSC+AE intervention will consist of the above described CTSC intervention with additional content and discussions related to NRT adherence. Specifically, the counselor will lead didactic discussions regarding the prevalent misconceptions associated with NRT use and quitting that have been identified among Latinos. For example, the counselor will discuss the common misconceptions regarding the health effects of the nicotine patch use. In addition to addressing misconceptions, the counselor will also explore the topic of smoking cessation medication use as it relates to several Latino cultural values, including health related fatalism, gender roles (machismo or marianismo), and health related bravado. Throughout the AE content the counselor will also aim to normalize the ambivalence that is often experienced with regard to quitting and the use of a nicotine products as an aid for cessation. In our preliminary work, participants noted a high degree of shame associated with their smoking as well as unsuccessful attempts at quitting and the use of NRT. The normalization of these areas will help to alleviate shame and offer alternative modes of reframing their affective experience. Lastly, specific strategies for enhancing medication adherence will also be discussed including techniques for self-reminding and monitoring. (See Appendix T for CTSC+AE manual).

The interventionist will be a master's level clinician with at least 2 years of clinical experience. [name] [name] (PI) will train and supervise the interventionist. Prior to the initiation of the study, [name] will conduct one-on-one training sessions with the interventionist which will cover the execution of the protocol specifically the treatment interventions. Training sessions will include role plays and feedback. Once the study is initiated, [name] will meet with the interventionist on a weekly basis to discuss any

emergent issues that need to be addressed through further training. [name] will review a random sample of 20% of the session audios and use a checklist based on the treatment manual to maintain treatment fidelity and address any therapist "drift". [name] is a licensed and practicing psychologist in the State of Texas and has had experience in conducting and supervising behavioral interventions in the context of smoking cessation trials.

## 7.0 Evaluation During Study

**These measurements will be taken during each counseling session visits at week 2 and 6, and at the 3 and 6-month follow-up visits.**

**Measures:** As noted previously, the assessment battery will be available in both English and Spanish languages. Based on our previous work with the proposed instruments, we estimate the battery of measures will take approximately 1.5 hours to complete at baseline and during the 3 and 6-month visits.

*Adverse Events Monitoring* Participants will be closely monitored for any adverse side effects. Each in person visit that participants attend will include comprehensive assessment of adverse events, side effects and medication tolerability. Any reported adverse events will be kept in a log by the counselor or research assistants and reported to the IRB as necessary (Appendix L). Throughout the entire study, participants will be reminded that if they experience any intolerable or problematic side effects, they should immediately contact [name] and discontinue using NRT. During the event that a participant has a mental health emergency during a study visit session, the present research assistant will follow the Mental Health Emergency Procedures instructions (Appendix P).

*Adherence* NRT adherence will be assessed using three methods: 1) The Timeline Follow-back (TLFB) (Appendix M) interview at monthly visits. In our preliminary studies we successfully used the TLFB to collect data on medication adherence. The TLFB is a calendar-based interview that asks participants to recall the frequency of substance use. The TLFB has been used extensively in assessing the use of a variety of substances and health behaviors. This interview procedure involves eliciting calendar guided recall and utilizing anchoring of dates to significant events. The TLFB is widely used in the field of substance use research and has been shown to be a reliable measure of daily activity associated with a variety of health behaviors. 2) Participants will be asked to keep an NRT calendar diary and bring in the diary for each study visit. Participants that bring in their diary (we expect some will not) will be given a new diary form that they can use to continue documenting their use of NRT. 3) Similarly, participants will also be asked to bring in their boxes of patches. For participants that return with patch boxes (we expect some will not), the clinical research assistant will conduct a count of used and unused patches. The NRT adherence variable will be computed as the proportion of days of NRT use over the number of patches made available.

*Satisfaction Survey of Session Elements* (Appendix Y) This is an investigator developed scale on a 5 point Likert scale to assess to the extent to which the participants were satisfied with various elements of the session content. The items reflect the content of the HE, CTSC, and CTSC-AE manuals.

*Smoking Status* will be assessed at each study visit. The *Society for Research on Nicotine and Tobacco (SRNT) Abstinence Status Questionnaire* (pre- and post-versions) will be used. It surveys tobacco use by the participant and persons within the participant's household and social surroundings. Our outcome measure will be self-reported 7-day point prevalence smoking abstinence verified by expired carbon monoxide testing using a Bedfont Micro+ Smokerlyzer®. This variable will be assessed at the 2 and 6-week sessions and at the 3 and 6-month follow-up assessments.

The *Fagerstrom Test for Nicotine Dependence* (FTND) is a widely used measure of nicotine dependence. The Heaviness of Use Index is composed from a portion of the items on the larger measure. Six questions from the Fagerstrom questionnaire will be used in this protocol.

The *Alcohol Quantity and Frequency Measure* assesses quantity and frequency of alcohol consumption and is adapted from Cahalan (1973).

*Sense of Control* balances claiming versus denying control statements for good and for bad events, cancels the agreement bias that commonly exists when using Likert-scaled items, and improves the validity of the sense of control measure.

*Religious Health Fatalism Questionnaire (RHFQ)* Religious Health Fatalism is defined as "the belief that health outcomes are inevitable and/or determined by God", and assess the association between Religious Health Fatalism and health behaviors among individuals.

*Bicultural Involvement Scale (BIS)* is a 24-item self-report measure used to assess cultural orientation. The measure generates scores for individuals' independent association with each of the two cultures, their degree of biculturalism, and a rating of their total cultural involvement. Originally developed for use with Hispanic and American individuals, the measure has also been modified for use with individuals from other cultures, including Asia and Australia. Adapted from the acculturation scale, the bicultural involvement questionnaire was developed by José Szapocznik, William M. Kurtines, and Tatjana Fernandez in 1980 as a multidimensional tool for measuring cultural orientation. Unlike the majority of acculturation measures that preceded it, the BIS does not assume that involvement in one culture necessitates exclusion of association with another.

*Fidelity Checklist (Appendix Z)* is an investigator developed checklist that mirrors the content of the HE, CTCS, and CTSC+AE treatment manual. This checklist will be used by the PI or his designee to review a random sample of 20% of the session audios, as

standard in monitoring fidelity of clinical trials, and document whether or not each element of the treatment manual was delivered by the interventionist. The Fidelity Checklist will provide descriptive data on content delivery to aid in modifying our intervention in subsequent studies. It will also be used as a tool for clinical oversight and the ongoing monitoring of interventionist. As needed, the PI will provide further training to the interventionist if substantial intervention "drift" is identified.

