## 4.0 Patient Eligibility

**Participants & Recruitment:** A total of 36 participants will be enrolled, 12 in each condition. We will recruit participants by posting flyers at locations in the greater Houston area that are known to be frequented by our target Latino population (ex: community centers, Hispanic food markets and grocery stores, salons, bus stations, clinics serving mainly Hispanics). We will also post ads in free Houston area Spanish language print newspapers (ex: La Subasta, Buena Suerte) as well as use radio ads heard throughout the greater Houston area. All ads and flyers will use the IRB approved advertisements. (See Appendix R).

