Demographics	20	
Medical History	5	
Tobacco History	10	
SRNT (Baseline or Post-Quit)	15	
Fagerstrom (FTND) – If non-abstinent	5	
Alcohol Quantity & Frequency	5	
Sense of Control	5	
Religious Health Fatalism	5	
Bicultural Involvement (BIS)	10	
Smoking Status	2	
Adherence-TLFB (Completed with RA)	10	92 minutes

*Demographics Questionnaire* (Appendix D) administered at baseline and follow-up will collect data on age, race, ethnicity, education, income, preferred language, and generations in the U.S. This questionnaire has been used extensively by our team.

*Medical History* (Appendix X) Participants will be asked to provide a detailed medical history including heart disease, asthma/lung disease, high blood pressure, diabetes, high cholesterol, thyroid problems, and kidney disease. Participants will also be asked to provide a detailed list of medications and their dosage that they take daily.

*Tobacco History* (Appendix E) collects information regarding onset of regular smoking, previous quit attempts, abstinence history, smoking rate, other household smokers, proportion of friends/family who smoke, and other tobacco use. This questionnaire has been used extensively by our team.

The *Fagerstrom Test for Nicotine Dependence* (FTND) (Appendix F) is a widely used measure of nicotine dependence. The *Heaviness of Use Index* is composed from a portion of the items on the larger measure. Six questions from the Fagerstrom questionnaire will be used in this protocol.

*Society for Research on Nicotine and Tobacco (SRNT) Abstinence Status Questionnaire* (pre- and post-versions) (Appendix G) surveys tobacco use by the

participant and persons within the participant's household and social surroundings.

The *Alcohol Quantity and Frequency Measure* (Appendix H) assesses quantity and frequency of alcohol consumption and is adapted from Cahalan (1973).

*Sense of Control* (Appendix I) balances claiming versus denying control statements for good and for bad events, cancels the agreement bias that commonly exists when using Likert-scaled items, and improves the validity of the sense of control measure.

*Religious Health Fatalism Questionnaire (RHFQ)* (Appendix J) Religious Health Fatalism is defined as "the belief that health outcomes are inevitable and/or determined by God", and assess the association between Religious Health Fatalism and health behaviors among individuals.

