Treatment Components Included in Both Conditions: Participants in all three arms of the study will receive Nicotine Replacement Therapy (NRT), which is the most commonly used and available smoking cessation pharmacotherapy. The use of NRT during a quit attempt is associated with a 50-70% increase in cessation rates. Thus, NRT is a well-established and empirically supported first-line treatment for individuals seeking pharmacotherapy for smoking cessation. Furthermore, when NRT is coupled with a behavioral intervention such as counseling, cessation rates substantially increase by up to 16%. Therefore, the combination of a behavioral intervention with NRT is widely considered an optimum level of treatment. All participants (CTSC, CTSC+AE and HE conditions) will receive 12 weeks of NRT patch treatment - Nicoderm CQ (GlaxoSmithKline, Philadelphia, PA). Participants will be advised to use the patch according to the standard tapering schedule: 4 weeks of 21 mg, 4 weeks of 14mg, and 4 weeks of 7mg patches. Patch dispensation will occur at study visits. Participants receive only the number of patches necessary to last until the next study visit plus several extra patches should a patch fall off, become torn, etc., or should the visit be delayed. Based on our previous research, providing subjects with only enough patches to last until the subsequent visit improves compliance. A reduction in dosage or cessation of the patch regimen will be implemented for any participant who shows signs of being on too high of a dose. This is typically necessary for very few participants because blood nicotine levels are usually much lower on the patch than while smoking.

 Self-Help Materials: Self-help materials will consist of the consumer products

developed for the *Treating Tobacco Use and Dependence Clinical Practice Guideline*.

During the first session and irrespective of treatment condition, the interventionist will work with the participant to set a quit date within two weeks (participant's willingness to set a quit date within 2 weeks is an inclusion criteria for the study). The process of setting a quit date will follow the *Treating Tobacco Use and Dependence Clinical Practice Guidelines* and the interventionist will engage in a discussion about the ideal date and the consideration of various scheduling factors (e.g., a weekend date versus weekday).

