## 11.0 Statistical Considerations

**Proposed Analyses:** In this pilot study, we will summarize descriptive statistics to characterize our study sample and describe between group differences. Descriptive statistics will be tabulated for all study variables which includes demographics, measures of intervention acceptability, feasibility, fidelity, and smoking history, nicotine dependence, and other variables.

We also plan to conduct basic effect size estimates to derive preliminary findings based on pre/post design. With such a small sample size, we will focus on the substantive magnitude of observed between group differences. We will, however report Fischer's exact p-values and the nonparametric Kruskal-Wallis test for equality of rank-ordered population distributions when comparing treatment groups on categorical and continuous outcomes, respectively. Graphical methods will also be used to explore and describe the association between adherence to treatment and smoking in each of the intervention groups.

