Aim 3 compares the three treatment groups (CTSC, CTSC+AE, & HE) on the mean percentage of days of NRT adherence during the 12 weeks of treatment. In our preliminary study of Latino smokers (Project Impact) we found that on average participants were adherent on 46.7% (standard deviation=36) of days during the 12 weeks of NRT treatment. Based on this finding, we estimate that our control condition (HE) will show a similar rate of NRT adherence (adherent on 56% of treatment days). We are guided primarily by our expectations that clinically significant improvements in outcomes will be achieved with >75% adherence and we base our estimate of the NRT adherence rate for our CTSC+AE condition on two studies reporting NRT adherence rates for interventions that sought to increase adherence but did not exclusively target adherence. The adherence rates of the experimental condition in these studies ranged from 88-93%. The current study is not only designed to test the feasibility of CTSC and CTSC+AE (Aim 1), but to evaluate the CTSC+AE intervention compared to HE and CTSC groups. It is not expected to be a definitive efficacy trial and the proposed sample will yield power to detect only large effects. We will have power to detect a conservative estimate of 80% adherence in our CTSC+AE condition. When we account for an attrition rate of 20%, a sample of 36 participants can detect a mean difference of 13% or greater between the groups using a 2-tailed alpha = .05. Due to the limited scope of this development project, this study will not be powered for formal hypothesis testing of group differences. Nevertheless, the proposed study will conduct analyses investigating distributional assumptions and co-variation among examined predictors which will inform the design of a future efficacy trial that will be fully powered. Lastly, we will explore potential mediators and moderators (AIM 4) of our primary outcomes and treatments using descriptive statistics, the chi2 test, and correlational analyses

including the bivariate Pearson r. This approach is unable to confirm a significant mediational or moderation effect. It was selected due to our limited sample size. However, our aim is to identify potential trends that can be further tested in a larger and subsequent study using standard mediational and moderation analytic approaches.

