- 3) Our primary research question compares the three treatment groups (CTSC, CTSC+AE, & HE) on the mean percentage of days of NRT adherence during the 12 weeks of treatment. In our preliminary study of Latino smokers (*Project Impact 1*) we found that on average participants were adherent on 46.7% (SD=36) of days during the 12 weeks of NRT treatment. Based on this finding, we estimate that our control condition (HE) will show a similar rate of NRT adherence (adherent on 56% of treatment days). We are guided primarily by our expectations that clinically significant improvements in outcomes will be achieved with >75% adherence and we base our estimate of the NRT adherence rate for our CTSC+AE condition on two studies reporting NRT adherence rates for interventions that sought to increase adherence but did not exclusively target adherence. The adherence rates of the experimental condition in these studies ranged from 88-93%. The current study is not only designed to test the feasibility of CTSC and CTSC+AE (Aim 1), but to evaluate the CTSC+AE intervention compared to HE and CTSC groups. It is not expected to be a definitive efficacy trial and the proposed sample will yield power to detect only large effects. Due to the limited scope of this development project, this study will not be powered for formal hypothesis testing of group differences. Nevertheless, the proposed study will conduct analyses investigating distributional assumptions and co-variation among examined predictors which will inform the design of a future efficacy trial that will be fully powered.
- 4) Other smoked non-tobacco substances can potentially interfere with our carbon monoxide testing. To address this concern, prior to all CO testing, participants will be asked whether they have smoked non-tobacco substances in the last two days. If so, the participant will be asked to provide an additional CO sample after 2 days of non-tobacco substance abstinence.

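### NRT adherence, the stated primary research question, has two unreconciled denominators: patches made available and days in the 12 weeks

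*Combined protocol and SAP*

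**What the plan says.** Section 7.0 (Adherence) defines the variable: "The NRT adherence variable will be computed as the proportion of days of NRT use over the number of patches made available". Aim 3 gives the same ratio in Section 1.0 and again in Section 11.0.

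The analysis text uses another scale. Section 11.0 compares the arms for Aim 3 on the "mean percentage of days of NRT adherence during the 12 weeks of treatment". Item 3 of Analytic and Design Considerations gives that comparison its status: "Our primary research question compares the three treatment groups (CTSC, CTSC+AE, & HE) on the mean percentage of days of NRT adherence". The planning figures beside both statements are percentages of days: 46.7% (SD 36) in the preliminary study and 56% assumed for the control arm. The same text expects that "clinically significant improvements in outcomes will be achieved with >75% adherence".

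On supply, Section 6.0 says "Participants receive only the number of patches necessary to last until the next study visit plus several extra patches". Sections 6.0 and 14.0 both have patches handed out at study visits. Item 6 of Analytic and Design Considerations counts days without data as non-adherent. Section 11.0 puts the emphasis on the size of between-group differences and adds the "nonparametric Kruskal-Wallis test for equality of rank-ordered population distributions" for continuous outcomes.

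**The concern.** The two definitions share a numerator, days of patch use, but not a denominator. No section equates them or says whether the patches made available are those actually issued or the whole planned course.

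If they are the patches issued, each participant's denominator depends on attendance after randomisation. The missing-data rule does not repair this, because it sets days of use to zero and leaves the patch count alone. Three things are then at stake:

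- whether results can be set beside the day-based planning rates and the 75% expectation;
- whether participants with different attendance are ranked on a common scale;
- whether the denominator could be chosen after the data are seen.

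**Working it through.** The plan gives no worked adherence score, so there is none to reproduce. Its detectable-difference figure is a separate matter and this point does not rest on it.

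**Inputs from the documents.** Supply visits at baseline, week 2 and week 6 (Section 1.0); a 12-week course, so 12 × 7 = 84 days; intervals of 14, 28 and 42 days to the end of the course.

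**Assumptions.** Patches start at baseline. Each supply is the interval plus k extras, with k = 2, 3 or 5, because the number of extras is not given. Leftovers are not netted off, and a missed visit is not made up.

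**Denominators.**
- Patches issued, all visits attended: 84 + 3k = 90, 93, 99.
- Patches issued, week 6 missed: 14 + 28 + 2k = 46, 48, 52.
- Day scale: 84 throughout.

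For any non-zero use, a full attender therefore scores lower on patches issued than on days, and a participant who misses week 6 scores higher.

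**Scores (%).**

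| Pattern | Days used | Issued, k=2 | k=3 | k=5 | Over 84 days |
|---|---|---|---|---|---|
| Daily use, all visits | 84 | 93.3 | 90.3 | 84.8 | 100 |
| Daily to day 42 then stops, all visits | 42 | 46.7 | 45.2 | 42.4 | 50.0 |
| Daily to day 42 then stops, misses week 6, days recovered | 42 | 91.3 | 87.5 | 80.8 | 50.0 |
| Same, days after week 2 not recovered | 14 | 30.4 | 29.2 | 26.9 | 16.7 |
| Steady 50% user, all visits | 42 | 46.7 | 45.2 | 42.4 | 50.0 |
| Steady 50% user, misses week 6, days recovered | 21 | 45.7 | 43.8 | 40.4 | 25.0 |

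Recovered means that the days are captured later, for example at the 3-month visit, where the Section 5.0 schedule repeats the timeline follow-back (TLFB) adherence interview. A participant who never returns after baseline scores 0 on both scales under the missing-data rule.

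**When missing week 6 raises the score above full attendance.** Let E be the days used in the first 42 days and T the days that would be used with full attendance. Missing week 6 raises the patches-issued score when E/(42 + 2k) > T/(84 + 3k), that is, when E/T > (42 + 2k)/(84 + 3k) = 46/90, 48/93, 52/99 = 51.1%, 51.6%, 52.5%. A steady user has E/T = 50% and falls just short. Someone who stops at day 42 has E/T = 100%. So use must drop after the missed visit, and the earlier days must be recovered.

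**Equal attendance and equal extras.** Every score is multiplied by 84/(84 + 3k). The planned 80% becomes 74.7, 72.3, 67.9 and the planned 56% becomes 52.3, 50.6, 47.5. The 24-point gap becomes 22.4, 21.7, 20.4, and the SD shrinks by the same factor. Ranks, the Kruskal-Wallis p-value and standardised effects do not change.

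**The case against.** The strongest reply is that the definitions can be read as one. Every participant is to receive 12 weeks of patches, and Section 11.0 states the analysis in days of those 12 weeks, so the patches made available could mean the planned 84. That reading is possible and removes the problem, but the text does not state it, and the supply rule points as easily to patches issued.

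A second reply is that the large case needs several things at once: near-daily use that stops at the missed visit, no rescheduling (item 6 promises exhaustive scheduling efforts, and extras are supplied against delayed visits), and later recovery of the days. This stands. The recall window of the adherence interview is in an appendix that is not in the text reviewed. Without recovery, the k = 3 score is 29.2%, below the 45.2% of a full attender with the same true use.

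A reader might infer that missed visits generally inflate scores, or that the between-arm comparison is biased in a known direction. The documents support neither. The steady-user rows run slightly the other way, and no missed-visit rate by arm is given.

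Third, this is a 36-person pilot that the plan says is not powered for formal testing. That limits the consequence but does not remove it, because magnitudes are what Section 11.0 says it will focus on.

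**Conclusion.** The conflict is in the current text and should be resolved before analysis. Its size depends on an undefined term. It is nil if the denominator is a fixed 84-patch course. If the denominator is patches issued, with 2 to 5 extras per supply and patches started at baseline, perfect use scores 93.3% to 84.8%. One pattern of 42 days of use can then score anywhere from 42.4% to 91.3% depending on attendance and extras, on either side of the plan's 75% expectation, while the day scale gives 50.0%.

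Confidence is high for the mismatch and for this arithmetic. Distortion between arms is a possibility whose size and direction cannot be derived from the documents. With equal attendance and extras, only the reported magnitudes change.

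**What to change.** In Section 1.0 (Aim 3), Section 7.0 (Adherence) and Section 11.0 (Aim 3), define adherence as days of patch use divided by a fixed 84 days, with the item 6 rule applied to days without data. This matches the scale already used in the Section 11.0 analysis text.

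State day 1 for the count, by one rule for all arms: for example the planned patch start or the set quit date, with baseline if none is set. This is needed because the quit date may fall up to two weeks after enrolment and the documents do not give the patch start day. If use began 14 days in and counting ran from baseline, perfect use could reach only 70/84 = 83.3%. This concerns the counting origin only, not when patches should start.

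Keep days per patch issued as a secondary descriptive measure. Report by arm how many participants stopped patches as Sections 6.0 and 7.0 provide.

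The cost is wording in three places and no new data collection, since both scales share a numerator. Scores fall for participants who miss visits. Days after protocol-directed stopping count as non-use, which is why that number should be reported by arm.
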